3.3.1 Painful Crises

Painful crisis is one of the two components of VOC events. For the definition of painful crisis and identification of number of painful crises within the treatment period please refer to Section 3.2.1.

In addition to number of painful crises, the total duration (days) of painful crises will be derived as follows:

Total duration (days): Defined as the sum of the duration (days) (taking into account overlapping painful crisis days + 7-day onset rule as described below) of painful crises experienced by a patient over the defined treatment period, where:

- Duration of event (days) = (stop date of event – start date of event) + 1
 Total duration (days) will be calculated as the sum of the duration (days) of each event. If two or more events have overlapping durations, the overlapping days will only be counted once. Events with an onset date ≤ 7 days of the previous event onset date will not be counted as a new event (7-day onset rule). (refer to Section 3.2.1).
 For example: Patient 1: 2 events with total duration (taking into account overlapping days = 0 + 7-day onset rule) of 14 days: Derived as the sum = 5 + 2 + 3 + 4 = 14

1. PAINFUL CRISIS	2019-07-24	2019-07-28	5 days
2. PAINFUL CRISIS	2019-10-22	2019-10-23	2 days

3. PAINFUL CRISIS	2019-10-28	2019-10-30	3 + 4 intermission days
-------------------	------------	------------	-------------------------

For example: Patient 2: 2 events with total duration (taking into account overlapping days = 1 + 7-day onset rule) of 16 days: Derived as the sum = (9 + 1 + 3 + 4) – 1 (overlapping day) = 16

1. PAINFUL CRISIS	2019-10-15	2019-10-23	9 days
2. PAINFUL CRISIS	2019-10-23	2019-10-23	1 day (overlaps with previous individual event so does not count toward total duration)
3. PAINFUL CRISIS	2019-10-28	2019-10-30	3 days + 4 intermission days

For summary purposes, patients who do not experience any painful crisis during the defined treatment period will have their duration of painful crisis set to 0 days.

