2.2 Secondary objectives

Secondary Objective:	Outcome Measure:
To compare the effect of ticagrelor vs placebo for the reduction of painful crises	Number of painful crises
To compare the effect on ticagrelor vs placebo for the reduction of ACS	Number of ACSs
To compare the effect of ticagrelor vs placebo for the reduction of duration of painful crises	Duration of painful crises
To compare the effect of ticagrelor vs placebo on the number of VOCs requiring hospitalisation or emergency department visits	Number of VOCs requiring hospitalisation or emergency department visits
To compare the effect of ticagrelor vs placebo on reduction of days hospitalised for VOC	Number of days hospitalised for VOC
To compare the effect of ticagrelor vs placebo on the number of acute SCD complications ^a	Number of acute SCD complications
To compare the effect of ticagrelor vs placebo on reduction of days hospitalised for acute SCD complications ^a	Number of days hospitalised for acute SCD complications
To compare the effect of ticagrelor vs placebo on the number of sickle cell-related red blood cell (RBC) transfusions	Number of sickle cell-related RBC transfusions
To describe the health-related quality of life (HRQL) and fatigue	HRQL total score and by dimension using Paediatric Quality of Life Inventory (PedsQL) SCD Module and Fatigue total score and by dimension using the PedsQL Multidimensional Fatigue Scale as presented in Appendix I (age appropriate versions)
To describe absence from school or work due to SCD	Proportion of days of absence from school or work (only if going to school or work at randomisation)
To describe intensity of pain during VOC	Intensity of worst pain daily during VOC - For patients ≤ 4 years of age, observer reported using the Face, Legs, Activity, Cry, Consolability Scale (FLACC) - For patient ages 5 to 18 years of age, self-reported using the Faces Pain Scale Revised (FPS-R)
To describe analgesics use during VOC	Type of analgesics (opioid and non-opioid) use

To describe patient acceptability of the formulation (palatability and swallowability)	
 - For patients ≤ 4 years of age taking the tablet dispersed or whole, an observer assessment of palatability and swallowability will be undertaken - For patients ≥ 5 years of age taking the tablet dispersed or whole, palatability will be assessed and categorised using the Facial Hedonic Scale
--	--

^a The acute SCD complications are defined in Section 5.1.5.

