3.2 Primary Efficacy Variable

3.2.1 Vaso-occlusive Crises (VOCs)

A VOC event occurring during the study (following randomisation at Visit 2) and, as judged by the investigator to fulfil the definition of the primary endpoint event, should be recorded by the investigator both as a primary endpoint event on the VOC1 eCRF and as an adverse event (AE) on the AE eCRF.

The primary efficacy variable is the number of VOC events during the treatment period. The number of VOC events is defined as the count of VOC events experienced by a patient over the defined treatment period (refer to Section 3.1.4), as assessed by the investigator and collected on the VOC1 eCRF. Any VOC event identified outside the defined treatment period will not be included in the primary analysis.

A VOC is the composite of a painful crisis and/or an acute chest syndrome (ACS) event.

Each component is defined as:

- A painful crisis is an onset or worsening of pain that lasts at least 2 hours, for which there is no explanation other than vaso-occlusion and which requires therapy with oral or parenteral opioids, parenteral non-steroidal anti-inflammatory drugs (NSAIDs), or other analgesics prescribed by a healthcare provider in a medical setting (such as a hospital, clinic or emergency room visit) or at home.

- ACS is an acute illness characterised by fever and/or respiratory symptoms, accompanied by a new pulmonary infiltrate on a chest X-ray.

A VOC event is identified as follows:

- Within each of the two separate components: Event with an onset date ≤ 7 days of the previous event onset date will not be counted as a new event. It will be composed of the start date of the first occurrence of the component in the event to the stop date of the last occurrence of the component in the event.

For example: Patient 1: *Counted as 2 events not 3 individual events*

PAINFUL CRISIS	2019-07-24	2019-07-28
PAINFUL CRISIS	2019-10-22	2019-10-23
PAINFUL CRISIS	2019-10-28	2019-10-30

- Across the two separate components: Event with an onset date ≤ 7 days of the previous event onset date will not be counted as a new event. It will be composed of the start date of the first component in the event to the stop date of the last component in the event.

For example: Patient 2: *Counted as 4 events not 5 individual events*

ACUTE CHEST SYNDROME	2019-07-17	2019-07-23
PAINFUL CRISIS	2019-07-17	2019-07-23
PAINFUL CRISIS	2019-10-04	2019-10-04
PAINFUL CRISIS	2019-10-21	2019-11-05

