4.2.8.3 Duration of Painful Crises

Descriptive statistics will be presented for the total duration (days) (taking into account overlapping painful crisis days + 7-day onset rule) of painful crises experienced by a patient over the defined treatment period by planned treatment group. Patients who do not experience any painful crisis will have their duration of painful crises set to 0.

If numbers allow, the total duration (days) (taking into account overlapping painful crisis days + 7-day onset rule) of painful crises will be analysed using the negative binomial regression model, as described in Section 4.2.6.1.

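### Duration of painful crises is analysed only as total crisis days per patient, so it measures crisis-day burden and cannot show whether crises are shorter

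*SAP*

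**What the plan says.** Protocol 2.2 sets the objective: "To compare the effect of ticagrelor vs placebo for the reduction of duration of painful crises". Number of painful crises is a separate objective in the same table. Protocol 8.5.2 sends both to the primary analysis method, if numbers allow, and does not define duration further.

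SAP 3.3.1 supplies the definition. For one event, "Duration of event (days) = (stop date of event – start date of event) + 1". For the patient, "Total duration (days) will be calculated as the sum of the duration (days) of each event". On overlaps, "If two or more events have overlapping durations, the overlapping days will only be counted once". Patients with no crisis are set to 0 days.

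The 7-day onset rule also applies. Under SAP 3.2.1 an event whose onset falls within 7 days of the previous onset is not new, and the merged event runs from first start to last stop ("It will be composed of the start date of the first occurrence of the component in the event to the stop date of the last"). The first worked example in SAP 3.3.1 accordingly credits its third record with "3 + 4 intermission days".

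SAP 4.2.8.3 gives descriptive statistics of this total and says that, if numbers allow, "the total duration (days) (taking into account overlapping painful crisis days + 7-day onset rule) of painful crises will be analysed" with the model of SAP 4.2.6.1, whose offset is log follow-up time. SAP 3.3.2 carries the same derivation over to ACS duration, which SAP 4.2.10.1 only describes.

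**The concern.** A sum over all of a patient's crises grows with the number of crises. If ticagrelor prevents crises and does not change the ones that still occur, the duration endpoint will show a reduction close to the one in the count endpoint. A reader who takes the objective at its word would read this as a second finding, that crises are shorter, when it largely repeats the first.

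The gap rule adds a separate distortion. In Protocol 8.5.1 the 7-day rule is only a counting rule: a close event is not a new episode. The SAP extends it to duration, so days on which no crisis was recorded enter the total. Start and stop dates are collected for every VOC (Protocol 5.1.1.1), so missing data do not force this choice.

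**Working it through.** **1. The SAP's own examples.** Inputs are the dates in SAP 3.3.1. Merge onsets 7 days or less apart, span each merged event from first start to last stop inclusive, and count overlapping days once.

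- Patient 1: 24–28 July is 5 days. The records of 22–23 and 28–30 October have onsets 6 days apart, so they merge to 22–30 October, 9 days. Total 5 + 9 = 14, as the SAP states. Recorded crisis days: 5 + 2 + 3 = 10.
- Patient 2: 15–23 October is 9 days. The record of 23 October has its onset 8 days after 15 October, so it opens a new event. The onset of 28 October is 5 days after that, so it merges to 23–30 October, 8 days. Total 9 + 8 − 1 overlapping day = 16, as the SAP states. Recorded crisis days: 9 + 3 = 12.

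Four gap days enter each total: 4/14 = 29% and 4/16 = 25% of the total, or +40% and +33% on the recorded days.

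**2. What triggers the merge in Patient 2.** The one-day record of 23 October lies wholly inside the 15–23 October crisis, and the SAP notes that it adds nothing to the total. Remove it and the onsets are 15 and 28 October, 13 days apart. Nothing merges, there are still two events, and the total is 9 + 3 = 12. A record said to contribute no days raises the total from 12 to 16.

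**3. Largest gap from one merge.** Two 1-day crises with onsets 7 days apart span 8 days against 2 recorded, so 6 gap days.

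**4. What the modelled ratio estimates.** Crisis days per patient-year = crises per patient-year × days per crisis. Hence, approximately,

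ratio of totals = crisis rate ratio × ratio of days per crisis.

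This was simulated with the design inputs of SAP 1.3: 154 patients, 2.0 crises per year on placebo, 50% reduction unless stated, follow-up uniform over 12 to 24 months. Five days per placebo crisis is an assumption, because the documents give no figure; the expected ratio does not depend on it. Lengths were summed without merging. As a check, 1,500 runs of the count analysis with the shape of 0.8 read as the negative binomial size gave 90.5% power, matching the SAP's figure of about 90%. Reading 0.8 as the dispersion gave 96.6%. The scenarios below used 600 runs each and dispersion 0.8.

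| Scenario | Rate ratio × length ratio | Simulated ratio of totals |
|---|---|---|
| A. Crises halved, length unchanged | 0.5 × 1.0 = 0.50 | 0.50 |
| B. Number unchanged, length halved | 1.0 × 0.5 = 0.50 | 0.50 |
| C. Crises halved, each 40% longer | 0.5 × 1.4 = 0.70 | 0.69 |
| D. Crises halved, each twice as long | 0.5 × 2.0 = 1.00 | 1.00 |

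In A the total-duration test was significant in 92% of runs. Repeating A with size 0.8 gave a ratio of 0.50 and 77% of runs significant. A and B cannot be told apart from this estimate, and C still reads as a reduction in duration.

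**5. Likely size of the gap effect.** With the same rates, size 0.8, a fixed crisis length (assumed) and no clustering beyond differences between patients, about 8.5% of placebo crises and 4.4% of ticagrelor crises merge.

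| Crisis length (assumed) | Inflation of total, placebo | Inflation of total, ticagrelor |
|---|---|---|
| 1 day | 24% | 12% |
| 2 days | 8% | 4.4% |
| 3 days | 3.6% | 1.9% |
| 5 days | 0.7% | 0.4% |
| 7 days | 0% | 0% |

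The treatment ratio moves by about 10% at 1 day (1.12/1.24 = 0.90), about 4% at 2 days, and 2% or less from 3 days on. True short-term clustering would raise these figures; the documents give nothing to size it.

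**The case against.** The SAP hides nothing. It names the variable total duration in both sections, defines it as a sum and prints the intermission days in its examples. A reader might infer that the variable is concealed or mislabelled; the text does not support that. Total crisis days is a legitimate burden measure, it suits the count model that Protocol 8.5.2 prescribes, and scoring crisis-free patients as 0 keeps the full randomised comparison. That stands. What it leaves unanswered is the separate objective on duration.

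The gap days follow from the episode definition in SAP 3.2.1, and spanning a merged episode is a coherent convention. That stands in part. The SAP does not apply the convention evenly: days hospitalised for VOC are summed over individual stays (SAP 3.3.3), and the counts of VOCs and of painful crises each have a sensitivity analysis that ignores spacing (SAP 4.2.6.3 item 2 and 4.2.8.1), whereas duration has none. Table 3 in SAP 6 does not list the extension of the rule to duration.

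A reader might also infer from the examples that totals are inflated by a third or more, or that gaps between all crises are added. Neither holds. The examples were built to show merging, and gaps enter only inside merged events: in Patient 1 the interval from 28 July to 22 October adds nothing.

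Finally, crisis number is reported beside duration, so a crude days-per-crisis figure could be formed afterwards. It would not be prespecified, its denominator would be open, and if taken from the planned total it would still contain gap days.

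**Conclusion.** The point holds as a mismatch between objective and variable. The planned ratio is about the rate ratio times the per-crisis length ratio, so under the design assumption of a 50% reduction it would be about 0.5 with no change in crisis length. It supports a statement about crisis-day burden and none about shorter crises.

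The gap rule is real but secondary. It adds 4 days in each SAP example and at most 6 per merge of two crises; under the assumptions above it shifts the treatment ratio little unless crises last only a day or two. It is tempting to treat the gap days as the cause of the main problem, but removing them would leave a total that still rises with crisis count.

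The consequence is limited. SAP 4.1.1 makes secondary tests exploratory, the duration model runs only if numbers allow, ACS duration is only described, and the primary analysis is untouched.

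**What to change.** 1. Label and interpret the modelled variable as total crisis days (burden), and state that it does not estimate crisis length.
2. Count only calendar days covered by a recorded crisis, or report the total with and without intermission days. Do the same for ACS duration. Either version makes visible the Patient 2 effect, where a record inside an earlier crisis adds four days.
3. Add a descriptive summary by arm of recorded crisis days per crisis, with the denominator stated, for example merged events as counted in SAP 3.2.1. The choice matters: Patient 1 gives 10/2 = 5.0 days on merged events, 10/3 = 3.3 on individual records, and 14/2 = 7.0 if gap days are kept.

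The cost is one derivation change and one descriptive row, from data already collected. The downside is that days per crisis is conditional on having a crisis after randomisation, so the arms are no longer compared as randomised and the summary should stay descriptive.

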3.3.2 Acute Chest Syndromes

Acute chest syndrome is one of the two components of VOC events. For the definition of ACS and identification of number of ACS events within the treatment period refer to Section 3.2. The total duration (days) of ACS events, is one the exploratory objectives of the present study, and will be calculated using the same rules as painful crises detailed in Section 3.3.1. Similarly, for summary purposes, patients who do not experience any ACS events during the treatment period will have their duration of ACS set to 0 days.

3.3.3 VOC Events Requiring Hospitalisation or Emergency Department Visits

For the definition of VOC events and identification of number of VOC events within the treatment period please refer to Section 3.2.1.

The number of VOC events requiring hospitalisation or emergency department visits is defined as the count of VOC events, experienced by a patient over the treatment period, for which the primary setting for VOC treatment is in-patient hospitalisation or emergency department as captured on the VOC1 eCRF.

In addition to number of VOC events requiring hospitalisation or emergency department visits, the total duration (days) hospitalised for all individual VOC events experienced by a patient during the treatment period will be derived as follows:

Total duration (days): Defined as the sum of the duration (days) of all individual hospitalisations (taking into account potential overlapping hospitalisation days of VOC components) during VOC events experienced by a patient over the treatment period for which the primary setting for VOC treatment is in-patient hospitalisation:

- Duration (days) = (individual hospital discharge date per VOC event – individual hospital admission date per VOC event) + 1

Where:

Hospital admission and discharge dates are captured on the AE eCRF.

For summary purposes, patients who do not experience any VOC event and patients who do not experience any VOC event requiring hospitalisation will have their number of days hospitalised for VOC events set to 0 days.

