- Date of any telephone contact
- Start and stop date/time of the event
- Primary setting for VOC treatment (eg, in-patient hospitalisation, short-stay outpatient unit, emergency department or self-treated)
- Start and stop date/time of any in-patient hospitalisation
- Treatments administered of the event
- Complete AE/SAE form.

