4.2.8.5 Number of Days Hospitalised for VOC Events

Descriptive statistics will be presented for the total number of days hospitalised (taking into account potential overlapping hospitalisation days of VOC components) for VOC events experienced by a patient over the defined treatment period by planned treatment group. Patients who do not experience any VOC event as well as patients who do not experience any VOC events requiring hospitalisation due to VOC will have their number of days hospitalised for VOC set to 0.

If numbers allow, the total number of days hospitalised for VOCs (taking into account potential overlapping hospitalisation days of VOC components) will be analysed using the negative binomial regression model, as described in Section [4.2.6.1](#).

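### SAP 3.3.3 sums VOC hospital days only where the primary treatment setting is in-patient, so VOC admissions recorded under another setting are left out, a limit the protocol endpoint does not have

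*SAP*

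**What the plan says.** **Protocol.** Section 2.2 gives the outcome measure as "Number of days hospitalised for VOC", with no condition on where the crisis was mainly treated. Section 5.1.1.1 lists two separate eCRF items for each event: "Primary setting for VOC treatment (eg, in-patient hospitalisation, short-stay outpatient unit, emergency department or self-treated") and "Start and stop date/time of any in-patient hospitalisation".

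**SAP, count of events.** Section 3.3.3 counts VOC events "for which the primary setting for VOC treatment is in-patient hospitalisation or emergency department as captured on the VOC1 eCRF". Short-stay outpatient unit is not in that list.

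**SAP, days.** The same section then defines total days hospitalised. It repeats the condition "over the treatment period, for which the primary setting for VOC treatment is in-patient hospitalisation" (those words, with the comma, are from the count definition; the days definition has them without it), and here the condition ends at in-patient, with no emergency-department alternative. The dates come from a different form: "Hospital admission and discharge dates are captured on the AE eCRF".

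**SAP, zeros.** Section 3.3.3 adds that "patients who do not experience any VOC event requiring hospitalisation will have their number of days hospitalised for VOC events set to 0 days". Section 4.2.8.5 carries the same convention ("will have their number of days hospitalised for VOC set to 0") and neither repeats nor lifts the condition on setting.

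**SAP, parallel endpoint.** Section 3.3.4 sums days for acute SCD complications wherever a hospitalisation is reported, with no condition on setting.

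**The concern.** The protocol endpoint is time in hospital for VOC. The SAP makes it depend on a single-valued field about the primary place of treatment, held on a form other than the one with the admission dates. If a child has a recorded admission for a VOC but the field says emergency department or short-stay unit, the dates are in the database and the derivation ignores them.

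The endpoint's level then depends partly on how sites complete one field. The two hospital-day endpoints follow different rules without a stated reason, and SAP Table 3 does not list the restriction as a change or clarification from the protocol. SAP 3.3.3 is also in tension with itself: it introduces the variable as days hospitalised for all individual VOC events, then narrows it. Because 4.2.8.5 does not repeat the narrowing, two programmers could derive different totals.

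**Working it through.** The documents give no figure for this endpoint, so there is nothing to reproduce. The check has three steps.

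**1. Can an event carry admission dates under another primary setting?**

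- Protocol 5.1.1.1 collects the setting and the dates of any in-patient stay as separate items, and lists in-patient, short-stay unit, emergency department and self-treated as distinct examples of setting.
- Every VOC is also recorded as an AE (Protocol 5.1.1.1). In-patient hospitalisation makes an AE serious (6.2), and SAEs carry hospitalisation and discharge dates (6.3.3).
- So an admitted VOC should have dates on the AE form whatever the VOC1 form says about setting. Nothing in either document rules out the combination or tells sites which setting to record for a child admitted through the emergency department.

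**2. What does the written rule do with such an event?**

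SAP formula: days = discharge date − admission date + 1, summed over VOC events whose primary setting is in-patient. Take a hypothetical patient with three separate VOC admissions:

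| Primary setting | Stay | Days | In SAP days | In SAP count |
|---|---|---|---|---|
| In-patient | 1 to 5 July 2019 | 5 | 5 | yes |
| Emergency department | 1 to 8 October 2019 | 8 | omitted | yes |
| Short-stay unit | 1 to 4 December 2019 | 4 | omitted | no |

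- SAP rule: 5 days and 2 events.
- Every reported admission: 5 + 8 + 4 = 17 days and 3 events.

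The patient's total is 5, not 0. The explicit zero rule works at patient level; the other two stays are simply missing from the sum.

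**3. How large could the effect be?**

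The share of VOC hospital days recorded under another setting is not in the documents. Let it be m_P on placebo and m_T on ticagrelor, assumed to lie between 10% and 30%. Mean days in an arm are multiplied by (1 − m), and the ratio of mean days, ticagrelor to placebo, by (1 − m_T)/(1 − m_P).

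| m_P | m_T | Multiplier of the ratio |
|---|---|---|
| 10% | 10% | 0.90/0.90 = 1.000 |
| 20% | 20% | 0.80/0.80 = 1.000 |
| 30% | 30% | 0.70/0.70 = 1.000 |
| 20% | 10% | 0.90/0.80 = 1.125 |
| 10% | 20% | 0.80/0.90 = 0.889 |
| 30% | 10% | 0.90/0.70 = 1.286 |
| 10% | 30% | 0.70/0.90 = 0.778 |

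Equal loss lowers the mean in both arms and leaves the ratio alone. The unequal rows show only how sensitive the ratio is; nothing in the documents points to them.

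**The case against.** The best defence is that primary may mean main, not first. A child admitted through the emergency department would then be recorded as in-patient, and few or no days would be lost. The SAP's own use of the field fits this, since it takes in-patient as the marker of a hospitalised VOC. This stands as a limit on size. A reader might infer that all admissions through the emergency department score zero days; the documents do not support that, because they do not say how sites code such a case. But they contain no instruction for the harmless coding either, so the endpoint rests on an unwritten habit.

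Further points on the other side:

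- **The zero rule.** It covers patients with no VOC requiring hospitalisation and is an ordinary no-event convention. It does not set an individual admission to zero. This is correct; the omission comes from the filter.
- **The parallel endpoint.** Complications use another form (ASCD), and no primary-setting item is described for them, so the filter may not have been available there. This weakens the charge of inconsistency but does not justify the filter for VOC.
- **Attribution.** The filter may help tie a stay to treatment of the VOC. A crisis arising during a stay for another reason could carry dates that include days unrelated to it, since prolonging an existing hospitalisation is also a seriousness criterion (Protocol 6.2). This stands. Dropping the filter is not free of risk, and the replacement rule needs an attribution check.
- **Bias between arms.** The trial is double-blind, and site coding habits give no documented reason for different losses by arm. This stands.

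**Conclusion.** The point holds as a defect in the derivation of a secondary endpoint. As written, SAP 3.3.3 leaves out any VOC admission whose primary setting is not in-patient, although the protocol endpoint has no such restriction and the dates are collected. An admitted VOC recorded as emergency department still enters the event count but adds no days; one recorded as short-stay is missed by both measures.

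The frequency is unknown, because primary setting is undefined. The expected direction is an understated mean number of hospital days, by whatever share of days is recorded under other settings. The 10% to 30% range is an assumption, not an estimate.

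A reader might go on to infer a biased treatment comparison. The documents do not support that: it would need the loss to differ by arm. SAP 4.1.1 makes testing of secondary endpoints exploratory, 4.2.8.5 fits the model only if numbers allow, and the primary analysis of VOC counts does not use this field. The change is worth making because it is cheap and restores the protocol's endpoint.

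**What to change.** Before unblinding, amend SAP 3.3.3 as follows:

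1. Sum in-patient days over every hospitalisation reported for a VOC, whatever the primary setting, counting overlapping days once, as 3.3.4 does for acute SCD complications.
2. Count any VOC with such an admission as requiring hospitalisation, in addition to those with an emergency-department primary setting.
3. Keep the derivation filtered on primary setting as a sensitivity analysis, and list the change in SAP Table 3.
4. Tabulate, blinded, the VOCs that have admission dates but a primary setting other than in-patient. This shows how much the rule matters.

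If unblinding has already taken place, report the unfiltered sum as a supplementary analysis.

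No new data are needed. The cost is that each admission on the AE form must be linked to its VOC and checked, so that days of a stay for another reason are not counted. The SAP formula already works with admission and discharge dates per VOC event, so the link is needed in any case; the attribution check is the added work.
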